6.5 EVALUATION OF PHARMACODYNAMIC PARAMETERS

The PD markers (hsCRP, fecal calprotectin, and total sTL1A) will be summarized using descriptive statistics: N, mean, SD, min, max, median, coefficient of variation as a percent (CV %), and Geometric Mean (GM) by CDx status.

Stool samples for analysis of fecal calprotectin will be collected prior to any bowel preparation. Subjects will receive instructions and stool sample supplies for collection at home.

Listings and descriptive statistics (n, mean [or geometric mean], median, SD, CV%, min and max) will be provided by treatment group for each biomarkers (fecal lactoferrin, hsCRP, total sTL1A) specified in the study protocol as follows:

- Baseline values
- Values at each post-baseline visit
- Change from baseline or fold change from baseline at each post-baseline visit, depending on the data distribution of a PD marker

- % Change from baseline at each post-baseline visit, as appropriate

In the case of multiple values in an analysis visit, data will be selected for analysis as described in Section 4.4. Graphs of change from baseline will be presented, as appropriate.

6.6 EVALUATION OF PHARMACOKINETIC PARAMETERS

PK parameters will be computed, as appropriate, from the individual serum concentrations using a non-compartmental approach. All PK parameters will be summarized using descriptive statistics: N, mean[or geometric mean], SD, min, max, median, CV %, and GM and GM CV%. Serum concentrations of PRA023 will be summarized.

6.7 EVALUATION OF IMMUNOGENICITY

The proportion of subjects with any sample positive for ADA and the proportion of subjects with any sample positive for neutralizing antibody (Nab) will be summarized by the study period and dose using descriptive statistics. The PRA023 concentrations from all subjects and subjects with no sample positive for ADA will be summarized to assess whether ADA has an impact on PRA023 exposure.

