### **9.2.4 Evaluation of Immunogenicity**

The proportion of samples positive for ADA and the proportion of subjects with any sample positive for ADA will be summarized by dose, when appropriate, using descriptive statistics. The PRA023 concentrations from all subjects and subjects with no sample positive for ADA will be summarized to assess whether ADA has an impact on PRA023 exposure.

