3.2 DETERMINATION OF SAMPLE SIZE

The study is planned to enroll approximately 50 subjects. The sample size will enable a statistical power of 80%, at 1-sided significance level of 0.025, to test against the null hypothesis of endoscopic improvement rate of 12%, assuming the endoscopic improvement rate for PRA023 is 27%.

The null hypothesis of an endoscopic improvement (decrease in SES-CD $\geq 50\%$) rate of 12% is based on a meta-analysis estimate of the upper limit of 95% CI of the observed placebo rate (95% CI) of 9.5% (7.1, 11.9) from multiple modern-era CD clinical trials with centrally read endoscopy and similar eligibility criteria. [1]

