6.2.2 SENSITIVITY ANALYSIS

In the sensitivity analysis, patients in FAS with missing SES-CD score at Week 12 will be considered as a non-responder for the endpoint of endoscopic improvement. The 95% confidence interval will then be calculated according to Wilson score method.

The proportion of subjects with endoscopic improvement for PP analysis set and associated 95% confidence intervals will also be estimated by the following subgroups:

- CDx status (CDx+ or CDx-)
- Number of prior biologic use (0, 1, or 2+)
- Disease extent (ileal only, colonic only, or both)
- Disease severity (baseline SES-CD ≤ 16, or > 16)
- Concomitant use of immunosuppressive including AZA, 6MP, and MTX (Yes, or No)
- Concomitant use of oral corticosteroids (Yes, or No)
- ADA status (positive, negative)

Given the small sample size of the trial, the results of subgroup analysis should be interpreted with caution. The forgoing analysis may be modified when the sample size in a subgroup is deemed too small.

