6.3 SECONDARY EFFICACY ENDPOINTS

6.3.1 DICHOTOMOUS OR BINARY ENDPOINTS

The definition of the dichotomous secondary efficacy endpoints (i.e., responders) are listed in Table 3 below.

Table 3 Definition of Secondary Binary Endpoints

Outcome	Measure	Definition	Analysis Timepoints
Clinical Remission	CDAI	Crohn's disease activity index [CDAI] < 150	Week 12
Endoscopic and clinical improvement	SES-CD and CDAI	Decrease in SES-CD ≥ 50% AND reduction in CDAI ≥ 100 points from Baseline, or CDAI < 150	Week 12
Biomarker and Clinical Composite Improvement	hsCRP and CDAI	Decrease in hsCRP or fecal calprotectin ≥ 50% from Baseline and reduction in	Week 12

		CDAI \geq 100 points from Baseline, or CDAI < 150	
Clinical Response	CDAI	Reduction in CDAI \geq 100 points from Baseline or CDAI < 150	Week 12
PRO-2 remission	Abdominal pain score and Stool frequency	Average daily abdominal pain score \leq 1 point and average daily stool frequency \leq 3 points with abdominal pain and stool frequency no worse than Baseline	Week 12
Normalization of hsCRP	hsCRP	hsCRP < ULN, among subjects whose baseline hsCRP \geq ULN	Baseline, Week 12
Normalization of fecal calprotectin	fecal calprotectin	fecal calprotectin < ULN, among subjects whose baseline fecal calprotectin \geq ULN	Week 12
Anti-drug antibody (ADA) and Neutralizing antibody (Nab)	ADA and Nab	Positive ADA at any time; Positive Nab at any time	Over time

Abbreviations: SES-CD, Simple endoscopy score for Crohn's disease; CDAI, Crohn's disease activity index; hsCRP, High sensitivity C-reactive protein; PRO-2, Two component patient-reported outcome; ADA, Anti-drug antibody; Nab, Neutralizing antibody.

The proportion of clinical remission in FAS will be analyzed according to the method similar to the sensitivity analysis for the primary efficacy endpoint, in the case of missing data in CDAI at Week 12. If the resulting lower limit of 95% confidence interval is greater than 16%, the observed remission rate for the placebo treated patients from multiple prior CD trials ([1], [7], [8], [9], [10]), the null hypothesis for the first secondary endpoint of clinical remission at Week 12 will be rejected at a 1-sided significance level of 0.025.

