7.1.6 TREATMENT EMERGENT ADVERSE EVENTS

7.1.6.1 Definition of Treatment Emergent Adverse Events

Treatment Emergent Adverse Events (TEAE) are defined as following:

- AE onset date \geq 1st study treatment date; or
- AE worsened on or after the 1st study treatment date

AEs recorded prior to the first infusion of study treatment will be considered non-treatment-emergent. All reported AEs (treatment-emergent or not) will be listed. Only TEAEs will be summarized.

AEs of special interest including infections, acute infusion reaction (within 1 hour of completion of infusion), and peri-infusion reaction (within 24 hours of completion of infusion) will be summarized based on a pre-specified MedDRA list.

AEs occurring in subjects who are considered immunogenicity positive will also be summarized.

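### The effect of ADA on PRA023 exposure is to be read from two nested groups, which understates it, most of all when ADA is uncommon

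*SAP*

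**What the plan says.** SAP 6.7 states how the question will be answered: "PRA023 concentrations from all subjects and subjects with no sample positive for ADA will be summarized to assess whether ADA has an impact" on exposure. Protocol 9.2.4 has the same sentence. I found no other method for this question in either document.

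ADA status is set per subject. SAP Table 3 (section 6.3.1) defines it as "Positive ADA at any time; Positive Nab at any time". The content of the concentration summary is left open: SAP 6.6 lists statistics for PK parameters, including geometric means, but for concentrations says only "Serum concentrations of PRA023 will be summarized".

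Elsewhere the SAP does look at ADA-positive subjects on their own. Section 6.2.2 estimates endoscopic improvement separately in ADA-positive and ADA-negative subjects. Section 7.1.6.1 adds that "AEs occurring in subjects who are considered immunogenicity positive will also be summarized".

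PK and ADA samples coincide at Weeks 0, 2, 6 and 12 (Protocol Table 2), at Weeks 18, 26, 42 and 50 (Table 3), six-monthly after Week 50 (Table 4) and at all three follow-up visits (Table 5).

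**The concern.** The two groups are not disjoint. Everyone without a positive ADA sample is also counted among all subjects, so most of the data are the same on both sides of the comparison. The ADA-positive subjects, whose exposure is in question, never have a column of their own. They appear only through the shift that they cause in the overall figure, and that shift shrinks as their share shrinks.

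PK and immunogenicity are both secondary objectives (Protocol 2.2). What is at stake is that a substantial fall in concentration in a few ADA-positive subjects could be reported as two nearly equal summaries and read as little or no impact.

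**Working it through.** **Inputs**

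- Number of subjects: "The study is planned to enroll approximately 50 subjects" (SAP 3.2).
- ADA-positive share p: not in the documents. Assumed range 4% to 50%.
- Ratio r of concentration in ADA-positive to ADA-negative subjects: not in the documents. Assumed 0.7, 0.5 and 0.2, that is, true losses of 30%, 50% and 80%.
- Between-subject CV of concentration: not in the documents. Assumed 30% and 50%, log-normal.

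The plan states no ADA rate, ADA effect or exposure variability, so it has no figure of its own to reproduce here.

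**Arithmetic means.** Let m be the ADA-negative mean. Then mean(all) = (1 − p)m + p·r·m, so

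mean(all) / mean(negative) = 1 − p(1 − r), and the visible loss is p(1 − r).

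Example: p = 0.10, r = 0.5 gives 1 − 0.10 × 0.50 = 0.95, a visible loss of 5.0% against a true 50%.

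**Geometric means.** On the log scale, log GM(all) = log GM(negative) + p·log r, so

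GM(all) / GM(negative) = r^p, and the visible loss is 1 − r^p.

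Example: 0.5^0.10 = 0.933, a visible loss of 6.7%.

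**Visible loss in the planned contrast (arithmetic / geometric)**

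| ADA-positive share (of 50) | True loss 30% | True loss 50% | True loss 80% |
|---|---|---|---|
| 4% (2) | 1.2% / 1.4% | 2.0% / 2.7% | 3.2% / 6.2% |
| 10% (5) | 3.0% / 3.5% | 5.0% / 6.7% | 8.0% / 14.9% |
| 20% (10) | 6.0% / 6.9% | 10.0% / 12.9% | 16.0% / 27.5% |
| 30% (15) | 9.0% / 10.1% | 15.0% / 18.8% | 24.0% / 38.3% |
| 50% (25) | 15.0% / 16.3% | 25.0% / 29.3% | 40.0% / 55.3% |

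A direct positive-to-negative ratio shows the true loss in every row.

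**Against ordinary scatter.** With 45 ADA-negative subjects, the standard error of the log geometric mean is √ln(1 + CV²) / √45. That is 0.294 / 6.71 = 4.4% at a CV of 30%, and 0.472 / 6.71 = 7.0% at 50%. At p = 10%, a halving (6.7% visible on geometric means) is about the size of the standard error of one of the two figures being compared. A reader scanning the table could easily take it for noise.

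**Medians.** In a log-normal simulation at p = 10%, the all-versus-negative difference in medians was 3.9% for a true loss of 50% and 4.0% for 80% (CV 30%), or 5.2% and 6.4% (CV 50%). When positives are few, the median hardly tells a moderate loss from a severe one.

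**ADA flag.** Because one positive sample at any time classifies the subject, samples drawn before ADA appeared count as ADA-positive. This pulls r towards 1, on top of the nesting.

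**The case against.** The strongest reply is that the information is weakened in presentation, not lost. Protocol section 9 promises listings of all individual data and names the number of observations and the arithmetic mean as standard statistics. If both are shown, the ADA-positive mean can be recovered: with 50 subjects averaging 95 and 45 negatives averaging 100 (arbitrary units), it is (50 × 95 − 45 × 100) / 5 = 50. On the log scale the nested contrast is exactly p times the direct one, so its own sampling error shrinks by the same factor. A larger CV in the all-subjects column would also be a hint: 34% against 30% for a halving at p = 10% and CV 30%. All this stands and lowers the seriousness. It does not make the stated contrast suit its stated purpose. Medians and ranges cannot be subtracted, and a planned analysis should not need back-calculation.

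The consequences of ADA for efficacy and for adverse events are examined directly elsewhere in the SAP. That is also true, but neither analysis concerns exposure.

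Three stronger readings are tempting and not supported:

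- A reader might infer that any ADA effect is diluted almost to nothing. That needs a low ADA rate, roughly 10% or less, and no rate is given. At 50% positive a halving still shows as 25% to 29%. Nor is the visible loss always p times the true loss: that holds for arithmetic means, while geometric means follow r^p and show more.
- A reader might infer that this summary informs the two extension doses. Protocol 1.5 bases both on modelled suppression of soluble TL1A, and neither document links the ADA summary to dose choice. The SAP also leaves the complete extension analysis to a separate plan (section 9).
- A reader might infer that a finding of no impact is likely, or that error rates suffer. The comparison has no test, threshold or decision rule, so the documents support only a risk of misreading.

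**Conclusion.** The point holds as a limited one. In both documents, the only stated method for judging ADA impact on exposure compares a group with its own subset and understates any effect. For a true halving, about 5% to 7% would be visible at 10% positive, 10% to 13% at 20%, and 25% to 29% at 50%. The formulas are algebra. The ADA shares, effect sizes and CVs are assumptions, because the documents give none. The practical risk is overlooking a real effect when ADA is uncommon. Error rates, power and the primary efficacy conclusion are untouched. It is a low-cost improvement to a descriptive secondary analysis and worth making.

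**What to change.** Replace the sentence in SAP 6.7 and Protocol 9.2.4, and carry the change into the separate extension SAP, as follows.

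1. Summarize PRA023 concentrations by nominal visit and dose in two mutually exclusive groups, ADA-positive and ADA-negative. An all-subjects column can stay for reference.
2. Where possible, separate ADA-positive subjects' samples into those before and those after the first positive result. Without this step, the any-time flag leaves some dilution in the new comparison too.
3. When positives are few, plot their individual concentration-time profiles over the ADA-negative distribution.
4. If a geometric mean ratio is reported, state how values below quantitation are handled. SAP 4.1 sets PK values below quantitation to 0, for which a log, and hence a usable geometric mean, does not exist. This matters most if ADA drives concentrations below the limit.

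The cost is one sentence in each document, one extra table column and, if needed, one figure. No new samples or visits are required. SAP section 1 already provides for documenting later changes, with their rationale, in the clinical study report.

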6.8 MISSING DATA HANDLING

6.8.1 NON-RESPONDER IMPUTATION (NRI)

For the responder analyses as described in Table 3 of Section 6.2, unless specified otherwise, subjects who do not have sufficient measurements to determine the endpoint will be considered as non-responders (i.e., non-responder imputation (NRI)). Specifically, all subjects who discontinue from the study at any time prior to the assessment timepoint (regardless of reason) or fail to have an adequate efficacy assessment at that timepoint will be considered a non-responder.

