## **6.7 Immunogenicity (Anti-Drug Antibody)**

Antibodies to PRA023 will be evaluated in blood samples collected from all subjects at the time points specified in the protocol (see [Section 6.1.1](#)). The detection and characterization of antibodies to PRA023 will be performed using a validated assay method by the Sponsor or Sponsor's designee. Instructions for the handling of ADA samples will be provided in the Laboratory Manual.

Blood samples will be screened for antibodies binding to PRA023 and the titer of confirmed positive samples will be reported. If confirmed positive, antibodies may be further characterized and/or evaluated for their ability to neutralize the activity of PRA023. Other analyses may be performed to verify the stability of antibodies to PRA023 and/or further characterize the immunogenicity of PRA023.

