The point estimate and 95% CI for the secondary efficacy endpoints will be calculated for FAS, while the missing values in the categorical endpoint will be imputed as non-responders. Subgroup analysis (defined in section 6.2.2) may be performed for clinical remission, endoscopic and clinical improvement, biomarker and clinical composite improvement, clinical response, and PRO-2 remission.

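### SAP Table 3 treats ADA and Nab positivity as responder endpoints without exempting them from non-responder imputation, so read literally a missing result counts as antibody-negative, in conflict with SAP 6.7 and 4.3

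*SAP*

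**What the plan says.** SAP 6.3.1 introduces its table with the sentence "The definition of the dichotomous secondary efficacy endpoints (i.e., responders) are listed in Table 3 below". The last row is ADA and Nab. It is defined as "Positive ADA at any time; Positive Nab at any time", and its analysis timepoint is over time rather than Week 12. In this row, then, the responder is the antibody-positive subject.

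Two places deal with missing responder endpoints:

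- SAP 6.3.1, for the secondary efficacy endpoints in the Full Analysis Set (FAS): "missing values in the categorical endpoint will be imputed as non-responders".
- SAP 6.8.1, whose scope is "For the responder analyses as described in Table 3 of Section 6.2, unless specified otherwise" (Table 3 actually stands in 6.3.1). The rule is that "subjects who do not have sufficient measurements to determine the endpoint will be considered as non-responders". It then covers subjects who discontinue before the assessment timepoint, whatever the reason, or who "fail to have an adequate efficacy assessment at that timepoint will be considered a non-responder".

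Two other sections bear on the same endpoint. SAP 6.7 plans a descriptive summary, by study period and dose, of the proportion of subjects with any ADA-positive sample and with any Nab-positive sample. It names no analysis set, denominator or missing-data rule. SAP 4.3 says that missing data are in general not imputed for descriptive statistics unless a method is specified, and it sends the reader to Sections 6.2 to 6.4 for missing efficacy data.

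Protocol 6.7 makes Nab a follow-on test. When an ADA result is confirmed positive, "antibodies may be further characterized and/or evaluated for their ability to neutralize the activity of PRA023". Protocol 9.2.4 describes the immunogenicity summaries without a missing-data rule.

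**The concern.** Counting a missing value as a non-response is conservative when response is a benefit, because a subject without data cannot help the drug. When the event is a positive antibody test the same rule works the other way: a subject without data is recorded as having no antibodies, and the reported incidence can only fall or stay the same.

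The proportions developing ADA and Nab are listed secondary endpoints (Protocol 3.2; SAP Table 1). Protocol 5.4 links immunogenicity to anaphylaxis, infusion reactions and delayed hypersensitivity, so an incidence biased downward errs on the unsafe side. ADA status is also used elsewhere. SAP 6.2.2 defines an ADA subgroup with only two categories, positive and negative, and SAP 7.1.6.1 summarises adverse events in immunogenicity-positive subjects. A subject with no result has no stated place in either.

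**Working it through.** The documents give no expected ADA or Nab rate and no expected number without a result, so there is no planned figure to reproduce. The check compares the two readings and then works out what the literal one does.

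**Step 1. A subject with no ADA result.**

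- Table 3 with 6.8.1 and the 6.3.1 imputation sentence: non-responder, hence not positive, and kept in the FAS denominator.
- SAP 6.7 with 4.3: no imputation. Whether the subject stays in the denominator is not stated.

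Section 4.3 gives way where a method is specified, and 6.3.1 specifies one for its own table. Section 6.7 gives none. So the only explicit missing-data rule that covers the row is the one that scores missing as negative.

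**Step 2. Formula.** Let N be the subjects in the analysis set, m those with no result, and x those observed positive.

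- Imputed rate: x/N
- Rate among evaluable subjects: x/(N − m)
- Gap: x/(N − m) − x/N = [x/(N − m)] × m/N, that is, the observed rate times m/N

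**Step 3. Numbers.** N = 50 is the planned enrolment (SAP 3.2), taken here as the FAS size. The values of m and the ADA rates of 10% to 60% are assumptions. The count x is the assumed rate times (50 − m), rounded.

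| m | Assumed rate | x | x/50 | x/(50 − m) | Gap (points) |
|---|---|---|---|---|---|
| 0 | any | any | same | same | 0 |
| 1 | 10% | 5 | 10.0% | 5/49 = 10.2% | 0.2 |
| 2 | 20% | 10 | 20.0% | 10/48 = 20.8% | 0.8 |
| 5 | 10% | 4 | 8.0% | 4/45 = 8.9% | 0.9 |
| 5 | 20% | 9 | 18.0% | 9/45 = 20.0% | 2.0 |
| 5 | 60% | 27 | 54.0% | 27/45 = 60.0% | 6.0 |

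**Step 4. The discontinuation clause.** SAP 6.8.1 also makes a non-responder of anyone who discontinues before the timepoint. The antibody row has no fixed timepoint, so the clause does not fit it cleanly. Applied literally, it could turn an observed positive into a negative. Each such subject would lower the rate by a further 1/50 = 2.0 points, which the table does not include.

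**Step 5. Nab.** Three kinds of subject can lack a Nab result:

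- ADA-negative subjects. Under tiered testing they have none by design, and counting them as Nab-negative is correct.
- Subjects with no ADA result. Their Nab status is unknown.
- Confirmed ADA-positive subjects not tested for Nab, which the wording of Protocol 6.7 allows. Their Nab status is also unknown.

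Only the last two are misclassified if scored as negative.

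**The case against.** The best defence is that the SAP never meant to impute antibody results. Immunogenicity has its own section, 6.7, which is descriptive and split by study period and dose; that is not the layout of a single Week 12 responder analysis in the FAS. Section 4.3 bars imputation for descriptive statistics unless a method is given. The 6.3.1 sentence is about efficacy endpoints, 6.8.1 speaks of an efficacy assessment at a timepoint and allows for exceptions, and an antibody test is not an efficacy assessment. On this view the row is merely misplaced in Table 3.

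The second argument is size. The event is a positive result at any time. Samples are due at Weeks 0, 2, 6 and 12 or early termination (Protocol Table 2), and again at 28, 56 and 84 days after dosing (Protocol Table 5). To have no post-dose result at all, a subject must miss every one of the post-dose samples. Even at 5 missing and a 20% rate, the gap of 2.0 points is small beside the Wilson 95% interval for 9/50, 9.8% to 30.8%. These proportions are also outside the hierarchical testing in SAP 6.10.

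Much of this stands. The intention may well be the one in 6.7, and the effect on ADA is probably small. What does not stand is that the text settles the matter. Table 3 labels its rows as responders, two places impute non-response for that table without an exemption, and 6.7 supplies neither a denominator nor a rule that would clearly override them.

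**Conclusion.** The point holds as an unresolved conflict within the SAP, in which the only explicit missing-data rule reaching the ADA and Nab row points in the favourable direction. If that rule is applied, the ADA rate is understated by the observed rate times m/N: nothing when every subject has a result, and about 0.2 to 6 points for 1 to 5 missing of 50 at rates of 10% to 60%. The rates and missing counts are assumptions. The comparison with evaluable subjects also assumes that those without a result resemble those with one.

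Three stronger conclusions that a reader might draw are not supported:

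- That immunogenicity will be understated. SAP 6.7 with 4.3 allows an analysis without imputation, and the sampling schedule may leave few or no subjects without a result.
- That the Nab rate is heavily understated. With an assumed 3 Nab-positive subjects and 5 missing, the denominator alone moves the rate from 3/50 = 6.0% to 3/45 = 6.7%, or 0.7 points. Anything larger depends on how many ADA-positive subjects go untested, which the documents do not say. An untested subject has no positive sample with or without imputation.
- That the bias is greatest in subjects who leave early. An early leaver with one negative post-dose sample counts as negative under either approach; that comes from short observation, not from imputation.

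No hypothesis test, power figure or efficacy result is affected.

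**What to change.** In the SAP:

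- Remove the ADA and Nab row from Table 3, or state in both 6.8.1 and the 6.3.1 imputation sentence that it is exempt. Correct the cross-reference in 6.8.1, since Table 3 is in 6.3.1.
- In 6.7, define the denominator as Safety Analysis Set subjects with at least one evaluable post-dose ADA sample, and report the number not evaluable.
- For Nab, keep ADA-negative subjects as Nab-negative, and show confirmed ADA-positive subjects without a Nab result in a separate not-tested row, never as negative.
- In 6.2.2, say how subjects without an ADA result are handled in the ADA subgroup, for example with a not-evaluable category.

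The cost is SAP wording and one or two extra table rows, with no new data collection. The reported immunogenicity may come out slightly higher. Whether Nab testing of confirmed positives should be mandatory in Protocol 6.7 is a separate question, and this fix does not depend on it.

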#### 4.4.3 Prohibited Medications

- Any marketed biologic therapy throughout the study
- IV corticosteroid for treatment of CD during the IP
- Oral corticosteroid (prednisone  $> 20$  mg/day or equivalent) for the treatment of CD during the IP
- Oral budesonide  $> 9$  mg/day or equivalent or beclomethasone  $> 5$  mg/day during the IP
- Any per rectal therapy including enema (e.g., 5-ASA, budesonide, corticosteroid) during IP, other than that required for endoscopy preparation during the IP.
- Systemic tacrolimus, systemic cyclosporine, oral mycophenolate mofetil (MMF), immunoadsorption columns (such as ProSORBA columns), D-penicillamine, leflunomide, Thalidomide, purified medicinal probiotics throughout the study
- Chronic use of NSAIDs or aspirin  $> 100$  mg/day during the IP
- Any investigational drug other than the study medication throughout the study

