#### 4.5 Removal of Subjects from Study

A genuine effort must be made to determine the reason(s) why a subject fails to return for the necessary visits or is discontinued from the study. This information and date must be recorded on the appropriate eCRF and on the Termination Sheet. Subjects MUST discontinue from the study for any of the following reasons:

- The subject decides that it is in his/her best interest. It is fully understood that all subjects volunteer for the study and that they may withdraw their consent to continue in the study at any time.
- Any AE, laboratory abnormality, or change in medical condition which, in the opinion of the Investigator, indicates that continued participation in the study is not in the best interest of the subject.
  - For potential drug induced liver injury (DILI), timely confirmation of initial liver-related laboratory abnormalities should be performed. Potential drug induced liver injury is defined as:
    - ALT/AST elevation  $>3$  x ULN, AND
    - Total bilirubin  $>2$  x ULN, without initial findings of cholestasis (elevated serum alkaline phosphatase), AND
    - No other immediately apparent possible cause of increased ALT/AST and total bilirubin, such as viral hepatitis A, B, or C; preexisting or acute liver disease; or other drug capable of causing the observed injury
  - Subjects with suspected DILI should be discontinued from the study
- Persistent non-compliance of the subject
- Pregnancy

- Use of any investigational drug therapy for CD excluding study treatment
- Treatment with biologic therapy for CD

The Investigator must notify the Medical Monitor by telephone or by email as soon as possible if any subject prematurely withdraws from the study. The date when the subject is withdrawn and the reason for discontinuation must be recorded in the eCRF. If a subject is “lost to follow-up” (fails to return for study visits), a reasonable effort should be made to contact the subject in order to determine why the subject failed to return. This information must be documented in the eCRF. If a subject is withdrawn from the study early (regardless of the cause) all of the end-of-study evaluations should be performed at the time of withdrawal, and the subject followed for 12 weeks after the last dose of PRA023, if possible, due to the long  $t_{1/2}$  of PRA023.

It is agreed that, for reasonable cause, either the Investigator or the Sponsor, Prometheus, may terminate this study.

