5.4.2 CONCOMITANT MEDICATION

Any medication with a start date prior to or on the first dosing date and continuing to take after the first dosing date, or started after the first dosing date will be considered concomitant medications. In addition, concomitant medications with a start date after the last dosing date (concomitant medication taken during the safety follow-up period) will be presented in the follow-up medication

listing, as appropriate. If the start date of a medication is incomplete or missing, the medication will be assumed to be concomitant medication, unless the incomplete start date (month and/or year) or the stop date (complete or incomplete) clearly indicate that the medication started prior to first dosing date or later than 30 days after the last dosing date. Medication with completely missing start and stop dates will be included in the concomitant medication summary. Additionally, the use of prohibited medications will be summarized and listed.

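### No rule says how prohibited Crohn's disease therapy during induction affects responder status: the FAS analyses count such subjects by their observed score, and the PP analysis leaves them to judgement

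*SAP*

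**What the plan says.** **What is prohibited.** Protocol 4.4.3 lists "IV corticosteroid for treatment of CD during the IP" among the prohibited treatments, together with oral steroids above stated limits and rectal therapy. Protocol 4.4.6 allows rescue medication only in the open-label extension (OLE).

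**What the protocol does about it.** Section 4.4.6 says that a subject who needs a new CD therapy should be withdrawn. The mandatory-discontinuation list in section 4.5 includes "Treatment with biologic therapy for CD", investigational CD therapy and persistent non-compliance. It does not name steroids.

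**What the SAP does about it.**
- Section 5.4.2: "the use of prohibited medications will be summarized and listed". No analysis consequence follows.
- Section 6.8.1 applies non-responder imputation to the Table 3 endpoints. The triggers are study discontinuation before the timepoint, or subjects who "fail to have an adequate efficacy assessment at that timepoint will be considered a non-responder".
- Section 6.2.2, the FAS sensitivity analysis of the primary endpoint: "patients in FAS with missing SES-CD score at Week 12 will be considered as a non-responder". Missingness is the only trigger.
- Section 6.3.1 analyses clinical remission in the FAS in a similar way, against a fixed 16%.
- Sections 6.2 and 6.2.1 run the primary test in the PP set. Section 4.2.4 removes subjects with significant deviations from that set. Section 5.6 gives examples (certain eligibility criteria, wrong product, two or more missed infusions, no evaluable Week 12 SES-CD) and says the list is not exhaustive. Prohibited medication is not among the examples.

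**The concern.** The trial has one arm, is open-label, and compares observed rates with fixed nulls of 12% and 16%. If a subject improves because of an added or increased steroid, no concurrent control arm absorbs that effect, and the response goes into the rate attributed to PRA023. Both confirmatory tests turn on small counts, so one credited response can decide a borderline result.

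The gap differs by analysis set. In the FAS the written rules settle the matter: an observed score is used. In the PP set they do not settle it. Whether such a subject stays in depends on a judgement about what is an important deviation, and in an open-label study that judgement may be made with the outcome in view.

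**Working it through.** **Inputs.** SAP 3.2: "The study is planned to enroll approximately 50 subjects"; "at 1-sided significance level of 0.025, to test against the null hypothesis of endoscopic improvement rate of 12" per cent; "assuming the endoscopic improvement rate for PRA023 is 27" per cent; power 80%. SAP 6.2.1 and 6.3.1: success if the lower 95% limit exceeds 12% (Wilson, PP) or 16% (FAS). The number of affected subjects k and their response rate q are not in the documents. I assume k = 2 or 5 of 50, and q = 30, 50 or 70%.

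**1. The plan's own figure.** n = (z_a·√(p0·q0) + z_b·√(p1·q1))² / (p1 − p0)², with p0 = 0.12, p1 = 0.27 and q0, q1 their complements, gives 46. With a continuity correction it gives 52, and the power at 50 is 78.7%. The stated 80% is therefore reproduced to within 2 points and is not in dispute.

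**2. Success thresholds at n = 50.** Wilson lower limit L = [p + z²/2n − z·√(p(1−p)/n + z²/4n²)] / (1 + z²/n), z = 1.96.

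| Endpoint | Count | L | Result |
|---|---|---|---|
| Endoscopic improvement (null 12%) | 10/50 | 11.2% | fail |
| | 11/50 | 12.8% | pass |
| Clinical remission (null 16%) | 13/50 | 15.9% | fail |
| | 14/50 | 17.5% | pass |

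**3. False-positive rate with no affected subject.** P(Bin(50, 0.12) ≥ 11) = 3.2%. P(Bin(50, 0.16) ≥ 14) = 2.2%. That 3.2% exceeds 2.5% is a property of the Wilson rule and a separate matter.

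**4. Affected subjects counted by score.** The total is Bin(k, q) + Bin(50−k, p0). For k = 2 and threshold r:

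P = (1−q)²·P(Bin(48, p0) ≥ r) + 2q(1−q)·P(Bin(48, p0) ≥ r−1) + q²·P(Bin(48, p0) ≥ r−2).

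The three tails are 0.0156, 0.0351 and 0.0719 for remission, and 0.0245, 0.0560 and 0.1152 for endoscopic improvement. For remission with q = 50%: 0.25×0.0156 + 0.5×0.0351 + 0.25×0.0719 = 0.039.

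| | None affected | k = 2, q = 30/50/70% | k = 5, q = 30/50/70% |
|---|---|---|---|
| Remission (at least 14/50) | 2.2% | 2.9 / 3.9 / 5.1% | 4.2 / 8.4 / 14.6% |
| Endoscopic (at least 11/50), kept and counted by score | 3.2% | 4.6 / 6.3 / 8.2% | 7.3 / 14.4 / 24.6% |

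Counted as non-responders instead, the rates are 1.6% (k = 2) and 0.9% (k = 5) for remission, and 2.5% and 1.5% for endoscopic improvement.

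**5. Does withdrawal close the gap?** Only in part. A dose increase in a subject already on a permitted steroid is not clearly a new therapy under Protocol 4.4.6, and section 4.5 does not name it. Nor does withdrawal settle the primary endpoint. The discontinuation trigger in SAP 6.8.1 is tied to Table 3, which does not contain endoscopic improvement on its own. Protocol Table 2 schedules an ileocolonoscopy at early termination, and SAP Table 2 assigns ileocolonoscopies on Days 71–98 to Week 12/ET. A subject withdrawn after the Week 10 infusion (target Day 71) may have missed no infusion and have an evaluable score. Such a subject meets none of the exclusions named in section 5.6, and section 6.2.2 would treat the score as observed.

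**The case against.** The strongest reply concerns the primary test. Taking a prohibited medicine is a protocol deviation, section 5.6 has deviations reviewed throughout the study, and its list is open. Such a subject may well be dropped from the PP set. With two dropped, the threshold stays at 11 of 48 and the false-positive rate is 2.5%, below the starting 3.2%. This stands. A reader might infer that the primary analysis always credits a steroid-driven response to PRA023. The documents do not support that; they leave the handling open.

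A reader might also count every affected subject as a certain responder who stays in the PP set. That gives 6.3, 11.5 and 19.7% for one, two and three subjects at the 12% null. The arithmetic is correct, but these are worst cases, and nothing in the documents supports a response rate of 100%.

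The protocol also gives real protection. Induction rescue is not permitted, biologic or investigational CD therapy and persistent non-compliance require discontinuation, and discontinuation before the timepoint is non-response for every Table 3 efficacy endpoint. This narrows the gap mainly to steroid, rectal or similar use in subjects who stay in the study, plus the early-termination endoscopy case.

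Finally, the documents do not say how the historical placebo trials handled rescue therapy, so how closely either approach matches the 12% and 16% benchmarks cannot be checked. That limits any claim about the net bias. It does not excuse the lack of a rule.

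**Conclusion.** The concern holds in a limited form. No passage makes prohibited CD therapy during induction a non-response. In the FAS (the section 6.2.2 sensitivity analysis and the Table 3 binary efficacy endpoints, including the confirmatory remission test) a subject who stays in the study with a Week 12 score is counted by that score. In the PP primary analysis, exclusion is discretionary.

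The size is unknown. The error rates above are illustrations that assume PRA023 adds nothing in the unaffected subjects and that affected subjects respond at 30 to 70%. The endoscopic figures also assume that the affected subjects are kept. With two subjects the inflation is modest; with five it could be large. This is a gap in the analysis rules that should be closed, not a flaw that invalidates the design.

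**What to change.** **SAP 6.2.2, 6.3.1 and 6.8.1.** State that subjects who start or increase a protocol-prohibited CD medication after Day 1 and before the Week 12 assessment are non-responders for the binary efficacy endpoints in the FAS, whatever the observed score.

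**SAP 5.6.** State before database lock how these subjects are handled in the PP set. Either name such use as an important deviation, which fits the exclusion logic of that set, or count them as non-responders there too. State whether the choice also applies to an early-termination endoscopy used as the Week 12 score.

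**Cost.** SAP wording only, since concomitant medication is already collected with dates. The response rate may be slightly lower. If affected subjects would otherwise have responded like the rest, counting them as non-responders cuts exact power for endoscopic improvement at a 27% rate from 83.0% (P(Bin(50, 0.27) ≥ 11)) to 78.5% with two affected (Bin(48)) and 70.4% with five (Bin(45)). Excluding them from the PP set costs the same with two (78.5%, threshold still 11) and less with five (81.2%, threshold 10 of 45).
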